### *Cognitive*

The Shipley Institute of Living Scale (SILS): This is a brief, well validated means of estimating intelligence quotient (IQ) (Zachary, 1991). The form consists of 60 items comprising 2 subscales, a vocabulary subscale (40 items) which asks subjects to indicate which of four words is most similar in meaning to the target word, and an abstract thinking subscale (20 items) wherein subjects are asked to fill in a letter or number to complete a pattern. The SILS will be administered at the screening session to check for baseline group differences, since cognitive measures are included as outcomes and are expected to differentially change with withdrawal across medication groups.

Computerized Testing: Cognitive testing, administered at *ad libitum* smoking baseline and the post-2 ½ day-abstinence final assessment, will include computerized tasks of sustained attention (ANAM Continuous Performance Task (CPT)); CANTAB Rapid Visual Information Processing (RVP)), executive function in including cognitive flexibility, cognitive control planning and decision-making (CANTAB Stockings of Cambridge (SOC), CANTAB Cambridge Gamble Task (CGT), ANAM Stroop); and memory/learning (Hopkins Verbal Learning Task (HVLT); Digit Span) (Owen *et al*, 1991) (Owen *et al*, 1990) (Wechsler, 2008) (Brandt, 1991) (Reeves *et al*, 2002). Parallel task versions will be used where available. These tasks were chosen for the cognitive domains’ sensitivity to DA(Ersche *et al*, 2011; Harmer *et al*, 2001; Lange *et al*, 1992; Levin *et al*, 2011; Mehta *et al*, 1999; Owen *et al*, 1992), or nicotine(Sahakian *et al*, 1989); engagement of PFC-striatal neurocircuitry (Chase *et al*, 2008; Clark *et al*, 2007; Cools *et al*, 2004; Ersche *et al*, 2011; Kim *et al*, 2006b; London *et al*, 2005; Mehta *et al*, 2000; Owen *et al*,

1991); impairment in smokers(Durazzo *et al*, 2012; Hughes, 2007); relevance to smoking outcomes(de Wit, 2009; Patterson *et al*, 2010); and proposed relevance as treatment targets for smokers(Sofuoglu *et al*, 2013).

### *Biochemical*

Genetics: Blood samples for DNA extraction will be collected at screening to examine whether the Val158Met single nucleotide polymorphism (SNP) of the COMT gene modifies the effects of nicotine. To protect confidentiality, each subject's blood sample will be encoded with a numeric designation and the name of the individual will be stored in a separate database. The samples will be transferred to the Genetic Laboratory at the VA medical Center for processing and storage.

Laboratory Bloods: Standard laboratory blood screening will include liver and thyroid function tests, CBC, serum electrolytes, BUN, creatinine, PT and PTT. This will be done at screening, again at the post-2 ½ day abstinence testing session and at the 1-week follow-up.

Urine screens: Urine pregnancy screens will be administered at screening, *ad libitum* baseline, prior to medication initiation, and prior to Smoking Choice Paradigm at the post-abstinence final session and at the 1-week follow-up. Urine drug screens will be administered at screening, *ad libitum* baseline, prior to medication initiation, and at the post-abstinence final session. Urine cotinine levels will be measured at baseline and check-in sessions and at post-abstinence testing session.

Serum estradiol and progesterone analysis: Serum estradiol and progesterone levels will be measured before the *ad libitum* smoking baseline and post-abstinence final session for use as covariates in our analysis, since female sex hormones may contribute to variation in women's response to nicotine or withdrawal (Allen *et al*, 2009b; DeVito *et al*, 2013) or women's smoking cessation ability (Allen *et al*, 2008a).

Plasma cotinine, 3-hydroxycotinine (3-HC), and nicotine levels: Plasma samples will be taken at the *ad libitum* smoking baseline session and at the post-abstinence final session. 3-HC is the main metabolite of cotinine and the ratio of 3-HC/cotinine, also known as the nicotine metabolite ratio, reflecting the rate of nicotine clearance. Smokers with high 3-HC/cotinine ratio (faster metabolizers) reported greater craving for cigarettes following overnight abstinence and greater nicotine-induced subjective drug effects, suggesting the 3-HC/cotinine ratio may influence the reinforcing effects from nicotine or experience of abstinence. Plasma nicotine levels will also be measured at baseline to confirm smoking status and at the post- abstinence session to confirm abstinence. Assays for nicotine, cotinine, and 3-HC levels will be performed in [name] laboratory. Briefly, nicotine, cotinine and 3-HC are measured using HPLC coupled to tandem mass spectrometry (LC/MS/MS) employing stable isotope labeled internal standards as previously described.

Alveolar carbon monoxide: A measure of expired CO levels will be taken at the beginning of each visit and during the Smoking Choice Paradigm. At the medication stabilization *ad libitum* check-in sessions, CO readings will be collected as a secondary measure of smoking levels. During the check-in sessions and final session during the abstinence period, CO readings  $\leq 8$ ppm will be used to verify compliance with smoking abstinence on the first morning check-in following overnight abstinence. This level was recommended by the SRNT Subcommittee on

Biochemical Verification to confirm overnight abstinence (Benowitz et al. 2002). At subsequent abstinence check-ins (across the 60 hr abstinence) the subject will be considered to have met the criteria for abstinence-related bonus payment if their CO is  $\leq 8$ ppm and has not increased since their prior abstinence visit.

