#### *Behavioral*

Smoking Choice Laboratory Paradigm: Nicotine self-administration behavior will be measured with the number of “puffs” from a cigarette chosen during the Smoking Choice Paradigm. This paradigm will be administered once at the post-abstinence visit.

*Apparatus*: Measures of smoking behavior will be obtained using a smoking topography device. Subjects will smoke through a plastic cigarette holder that is fitted to the filter end of a cigarette and connected to a smoking topography device (CreSS from Plowshare Technologies). The cigarette brand will be the choice of each subject and will be provided by the investigator.

*Sample Smoking*: The sample smoking will be administered using a Directed Smoking Procedure. In this procedure, the puff duration (3 sec), the interval between 2 puffs (20 sec), and the puff volume (40 cc) are predetermined to minimize the variation in the amount of cigarette smoke inhaled across smoking choices (Zacny et al, 1987). The selected puff volumes reflect the average puff volumes in female smokers (Battig et al, 1982; Eissenberg et al, 1999; Hofer et al, 1992). To take puffs of a cigarette, subjects will light a cigarette, without inhaling, and insert it into the cigarette holder. A tone will guide subjects as to when to start and end inhaling each puff. When puff volume reaches the target volume, a tone will sound indicating that the subject should stop inhaling.

*Paradigm Procedure*: Participants will complete this paradigm in a designated, negative pressure room in our laboratory. The Smoking Choice Laboratory Paradigm will offer participants 2 sample ‘puffs’ followed by 10 additional smoking opportunities (2 ‘puffs’ per smoking opportunity) spanned across 90 minutes, for a total of 12 “puff” opportunities, wherein tokens can be exchanged for money (\$0.75/token) or 2 cigarette puffs. If participants choose cigarette puffs instead of money at every opportunity, they will smoke the equivalent of slightly more than one cigarette within the 90-minute laboratory paradigm.

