Official Title in ClinicalTrials.gov: Treatment for Nicotine Addiction in Women

NCT: NCT02448654

Document Date: 7/7/14

<from originally planned analysis section- from grant>

Sample Size Considerations and Data Analysis

Power Analysis: As this is the first randomized clinical trial evaluating the effect of tolcapone on withdrawal, smoking urges, and cognition in women smokers during abstinence, we used effect sizes from comparisons of Val158Met genotype as general proxies for treatment differences. In previous research, we found significant differences in women smokers by Val/Val vs. Met/_ genotype in withdrawal (F= 5.7, df=48, p=.02), smoking urges (F= 16.9, df=48, p<.001), and sustained attention (F=9.9, df=48, p=.003) during abstinence, and subjective ratings of nicotine's anxiolytic effects (F=3.7, df=47, p=.02) (see Preliminary Data). Using G*Power, we found that with a sample of 60, alpha=.05, power=.80, we would be able to detect large effects for our planned analyses (f=.37). We expect to enroll 80 subjects to achieve a completion N=60. However, with N=52 we would still be able to detect a large effect size (f=.40).

Analysis Plan: The primary statistical models will be analysis of covariance (ANCOVA) to test for medication group differences in withdrawal, smoking urges, sustained attention and smoking choice post-abstinence. COMT genotype will be used as an independent variable in an exploratory two factor ANCOVA. Menstrual cycle phase, race and baseline smoking severity will be included as covariates.

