Specific Aim 1: ANCOVAs will examine the effect of tolcapone on reducing a) withdrawal severity (MNWS); b) smoking urges (BQSU); and c) cognitive impairment (e.g., CPT) during abstinence vs. placebo. With 80% power, we can detect a large medication effect (f=.37). Specific Aim 2: ANCOVA will examine the effect of medication vs. placebo on laboratory smoking choices post-abstinence. With 81% power, we can detect a large effect (f=.40). Exploratory Aim 1: ANCOVAs will examine the effect of Met/_ genotype on reduced a) withdrawal severity (MNWS); b) smoking urges (BQSU); and c) cognitive impairment (e.g., CPT) during abstinence vs. Val/Val. With 80% power, we can detect a large genotype effect (f=.37). Exploratory Aim 2: ANCOVA will assess withdrawal and smoking post abstinence, using both medication and genotype as the independent variables and co-varying for baseline scores, to test for a medication by genotype interaction. With 81% power, we can detect a large effect (f=.40).

Exploratory Aim 3: Structural equation modeling will examine moderating effects of gonadal hormone levels on withdrawal severity and smoking behavior post-abstinence. The mediation effect size is unknown.

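### The baseline nicotine metabolite ratio is assayed before randomisation and given a prognostic rationale, but no SAP model uses it, so the smoking-urge and smoking-choice ANCOVAs may give up some precision

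*Protocol*

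**What the plan says.** - **The measurement.** The protocol's Biochemical section (plasma cotinine, 3-HC and nicotine) takes plasma at the ad libitum baseline and at the final session and assays all three analytes by LC/MS/MS. The Overview and Study Procedures place randomisation after the ad libitum session, so the baseline ratio is a pre-randomisation value planned for every randomised woman.
- **The rationale.** The same section reports that smokers with a high ratio had more craving after a night without cigarettes and stronger subjective nicotine effects, "suggesting the 3-HC/cotinine ratio may influence the reinforcing effects from nicotine or experience of abstinence".
- **The models.** The SAP Analysis Plan specifies ANCOVA for withdrawal, urges, sustained attention and smoking choice: "Menstrual cycle phase, race and baseline smoking severity will be included as covariates". Outcome baseline scores are mentioned only under Exploratory Aim 2. The ratio appears in no model.
- **The allocation.** The urn randomisation in Study Procedures balances race, smoking rate and cycle phase. It does not balance the ratio.
- **Smoking choice.** "This paradigm will be administered once at the post-abstinence visit", so this outcome has no baseline of its own.
- **Planned power.** The SAP states: "with a sample of 60, alpha=.05, power=.80, we would be able to detect large effects for our planned analyses (f=.37").

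**The concern.** The protocol gives a reason to expect the ratio to predict the constructs of Aims 1 and 2 and pays for the assay, but never says what the value is for. The neighbouring paragraph on estradiol and progesterone gives a similar rationale and does assign those hormones a covariate role. The ratio has the rationale without the role.

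Precision is what is at stake. A baseline variable that predicts the outcome, entered in the ANCOVA, reduces residual variance and narrows the interval for the medication effect. The trial is powered only for large effects and plans for substantial attrition ("We expect to enroll 80 subjects to achieve a completion N=60"), so a precision gain that needs no extra visit or sample is worth considering. There is also a timing point: a covariate chosen after the data have been seen carries less credibility than one fixed in advance.

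**Working it through.** **Inputs from the documents.** N = 60 completers, alpha = .05, f = .37 (SAP, Power Analysis); three listed covariates (SAP, Analysis Plan).

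**Assumptions.** 1:1 allocation (the ratio is not stated); one degree of freedom per covariate; a linear model. R² is the share of outcome variance that the metabolite ratio explains beyond the three listed covariates. No value is given, so .03 to .15 is an assumed range.

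**Step 1: reproduce the plan's figures.** Power comes from the noncentral F with 1 numerator df, noncentrality λ = f²N, and error df = N − 2 − (number of covariates).
- f = .37, N = 60: λ = .1369 × 60 = 8.214. Power is 80.5% with no covariates (58 df) and 80.4% with three (55 df). The SAP's 80% reproduces.
- f = .40, N = 52: λ = .16 × 52 = 8.32. Power is 80.7% with three covariates (47 df). This reproduces the SAP's N = 52 fallback and matches the 81% quoted for smoking choice. At N = 60, f = .40 would give 86%.

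Neither stated figure relies on the metabolite ratio.

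**Step 2: the cost of adding the ratio.**
- Degree of freedom: error df falls from 55 to 54. At unchanged λ, power goes from 80.39% to 80.37%, which is negligible.
- Chance imbalance: the ratio is not balanced at randomisation. With p covariates that differ between arms only by chance, the expected variance inflation of the adjusted difference is (N − 3)/(N − 3 − p). Going from p = 3 to p = 4 at N = 60 multiplies the variance by (57/53)/(57/54) = 54/53 = 1.019.

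**Step 3: the net effect.** Equivalent N = 60 / [(1 − R²) × 1.019], λ = .1369 × equivalent N, 54 error df.

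| Assumed R² | Equivalent N | λ | Power | Gain in women |
|---|---|---|---|---|
| not in model | 60.0 | 8.214 | 80.4% | – |
| 0 | 58.9 | 8.062 | 79.6% | −1 |
| .03 | 60.7 | 8.311 | 80.8% | about 1 |
| .05 | 62.0 | 8.486 | 81.6% | about 2 |
| .10 | 65.4 | 8.958 | 83.6% | about 5 |
| .15 | 69.3 | 9.485 | 85.7% | about 9 |

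**Step 4: break-even.** The variance gain equals the imbalance cost when 1 − R² = 53/54, so R² = .019, a partial correlation of about .14. Below that there is no net gain. At R² = 0 the loss is 0.8 of a power point.

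**Step 5: sensitivity to failed assays.** If women without a ratio drop out of the model, equivalent N uses the smaller n.
- R² = .03, one woman lost: 59 / (.97 × 53/52) = 59.7.
- R² = .05, two women lost: 58 / (.95 × 52/51) = 59.9.

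Both fall below 60, so one or two failed assays cancel the gain at the low end of the range.

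**The case against.** The strongest reply is that this is a preference among covariates and not a defect. The three listed covariates correspond closely to the urn-balancing factors, and adjusting for what was balanced is a coherent rule. Omitting a further predictor from a randomised comparison introduces no bias and leaves the type I error and the stated power intact. That stands, and it limits the point to efficiency.

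The second reply is that the benefit is unknown. The protocol says only that the ratio may have an influence and gives no correlation. What counts is the increment beyond smoking severity, race and cycle phase, which is also not given. That stands too, and is why the gain is shown over a range that runs down to nil.

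The third reply is that the change is not free: a missing assay would drop a woman from a complete-case model, and the SAP has no missing-data rule. Step 5 confirms this. It is an argument for keeping those women in the model, not for leaving the ratio out.

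Three stronger readings are tempting but go beyond the documents:
- **That smoking choice suffers most because it has no baseline.** The primary withdrawal and urge models list no outcome baselines either, so as written choice has no special disadvantage. The protocol's evidence on the ratio is most direct for craving. Its bearing on puffs chosen over money after 60 hours is inferred through reinforcement.
- **That withdrawal severity must benefit as well.** The evidence cited is for craving and subjective drug effects. Extending it to the MNWS total is inference.
- **That the IQ score is a parallel failure.** The protocol says "The SILS will be administered at the screening session to check for baseline group differences". It sets no significance rule and does not say that a covariate would be added afterwards, and the sustained-attention tasks have their own baseline.

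**Conclusion.** The point holds as a modest, conditional one. A pre-randomisation measure with a prognostic rationale in the protocol is used in no model and is not balanced in the allocation. The urge and smoking-choice ANCOVAs may therefore be somewhat less precise than the collected data allow. It should not be read as a bias, an error in the sample size, or a demonstrated loss.

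The gain runs from nothing at R² near .02 to about 5 points of power at R² = .15. The downside if the ratio proves uninformative is under one point. This rests on the assumed R², equal allocation and one degree of freedom per covariate. Race and cycle phase may use more, and the protocol names premenstrual symptoms and gonadal hormones as further covariates, so the true error df may be lower than 54. It also treats the bounded puff count as linear.

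**What to change.** In the SAP Analysis Plan, before unblinding:

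1. Prespecify log(3-HC/cotinine) from the ad libitum baseline sample as a covariate in the BQSU and smoking-choice ANCOVAs. Its use for MNWS is optional. Alternatively, state why the ratio is left out.
2. Say explicitly that the Day 8 sample is not used for this purpose, because it is taken after randomisation and during treatment.
3. State that women with a failed or missing baseline assay stay in the model, for example by simple imputation of this baseline covariate.

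An IQ covariate for sustained attention can be considered separately and is not needed here.

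The cost is a few lines of SAP text, one error degree of freedom per model and a small expected variance inflation (54/53). No new visit, sample or assay is required.

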#### *Physiological*

Vitals: Heart rate and blood pressure will be collected once at each visit and again at the end of the Smoking Choice Paradigm.

#### *Behavioral*

Smoking Choice Laboratory Paradigm: Nicotine self-administration behavior will be measured with the number of “puffs” from a cigarette chosen during the Smoking Choice Paradigm. This paradigm will be administered once at the post-abstinence visit.

*Apparatus*: Measures of smoking behavior will be obtained using a smoking topography device. Subjects will smoke through a plastic cigarette holder that is fitted to the filter end of a cigarette and connected to a smoking topography device (CreSS from Plowshare Technologies). The cigarette brand will be the choice of each subject and will be provided by the investigator.

*Sample Smoking*: The sample smoking will be administered using a Directed Smoking Procedure. In this procedure, the puff duration (3 sec), the interval between 2 puffs (20 sec), and the puff volume (40 cc) are predetermined to minimize the variation in the amount of cigarette smoke inhaled across smoking choices (Zacny et al, 1987). The selected puff volumes reflect the average puff volumes in female smokers (Battig et al, 1982; Eissenberg et al, 1999; Hofer et al, 1992). To take puffs of a cigarette, subjects will light a cigarette, without inhaling, and insert it into the cigarette holder. A tone will guide subjects as to when to start and end inhaling each puff. When puff volume reaches the target volume, a tone will sound indicating that the subject should stop inhaling.

*Paradigm Procedure*: Participants will complete this paradigm in a designated, negative pressure room in our laboratory. The Smoking Choice Laboratory Paradigm will offer participants 2 sample ‘puffs’ followed by 10 additional smoking opportunities (2 ‘puffs’ per smoking opportunity) spanned across 90 minutes, for a total of 12 “puff” opportunities, wherein tokens can be exchanged for money (\$0.75/token) or 2 cigarette puffs. If participants choose cigarette puffs instead of money at every opportunity, they will smoke the equivalent of slightly more than one cigarette within the 90-minute laboratory paradigm.

This paradigm represents a slight adaptation from the Smoking Choice Laboratory Paradigm that our group has previously used by our group (e.g., (Sofuoglu et al, 2009)). In prior studies, the 10 puff (in exchange for token) opportunities were spaced by 15 minutes each, therefore spaced over a duration of 2hr15 minutes. In this version the puff opportunities will be spaced by 9 minutes to condense the 10 puff opportunities into 90 minutes, to reduce subject burden. Since the total number of puffs will remain the same as prior protocols and will amount to only slightly more than one cigarette, this dosing remains moderate. If participants self-administer every puff offered, the cigarette will still be spread over much more time than most smokers would use to smoke a single cigarette (which normally lasts 5-10 minutes, rather than 90 minutes).

#### **D. Drugs**

Tolcapone: Generic tolcapone will be purchased by the Research Pharmacy from McKesson

## COMT Inhibition as a Novel Treatment for Nicotine Addiction in Women

Corp. Following oral administration, tolcapone reaches peak plasma levels within 1.5-2.0 hours and maximum inhibition of COMT activity in red blood cells is observed in 1-4 hours (Jorga, 1998; Jorga *et al*, 1998; Mannisto and Kaakkola, 1999).

Tolcapone's primary clinical use is in Parkinson's disease, as an adjunct to dopaminergic medications (e.g., levodopa) to optimize the balance and transitions between "on" and "off" states. In our study, smokers will take tolcapone at 100 mg dose three times a day (TID) for 7 days, and will receive a 100 mg dose on Day 8. Dose administration will be spaced by approximately 6 hours. Medication administration and oversight during the approximately one-week trial will be carefully monitored by our study nurse and physician.

*Justification for the tolcapone doses:* This dosing schedule is consistent with the manufacturer's recommended use of tolcapone. Previous recent studies with significant effects of the manipulation without problematic adverse drug effects began at 100mg TID for the first day then increased to 200mg TID (Apud *et al*, 2007; Grant *et al*, 2013), so our dosing is more conservative relative to these recent studies. Our dosing schedule is chosen to provide enough time to reach steady-state tolcapone levels (approximately 5 half-lives of tolcapone) prior to initiation of the abstinence period, then provide continued administration during the abstinence period.

Placebo: To maintain the double-blind, placebo pills will be designed to be visually identical to the tolcapone pills, and contain 25mg riboflavin to match the urine discoloration produced by tolcapone.

